5.4.1.1.5. Study treatment completion/discontinuation

Discontinuation from study treatment in the core study is used as derived in the core study. See the core study SAP for details.

Study treatment discontinuations in the extension study are collected on the extension eCRF page 'Premature Discontinuation of Study Treatment'.

A premature permanent treatment discontinuation in the extension study is defined as permanently stopping treatment prior to the extension EOT visit (Week 240/Week 288 for those Ukraine subjects, or at the time ponesimod is commercially available for treatment of MS in the subject's country, whichever occurs first).

Reasons for premature treatment discontinuation in the extension study are as follows:

- Death:
- Lost to follow-up;
- Pre-specified study treatment discontinuation criteria;
- Subject decision (further split into: Adverse event, Lack of efficacy, No reason provided, Other);
- Physician decision (further split into: Adverse event, Lack of efficacy, Other);
- Sponsor decision (further split into: Study termination, Other).

Study treatment completion records are collected on the extension eCRF page "Maintenance Ponesimod" where fields "Completed as per protocol" or "Approved Drug Available For Indication" are entered.

5.4.1.1.6. Study treatment interruptions

Study treatment interruptions in the core study is used as derived in the core study.

Temporary treatment interruptions refer to any period of time between a temporary study treatment end date and subsequent study treatment start date during which the subject did not receive study treatment. When considering the Combined Analysis Period, the time between end of treatment in the core study and start of treatment in the extension study is also a treatment interruption. The cumulative duration of all such treatment interruptions is derived for each subject.

In addition, for each subject, the number of interruptions > 3 days is counted.

5.4.1.1.7. Re-initiation of ponesimod

Re-initiations during the extension study are defined as any up-titration in the study drug log with a treatment gap of > 3 days before the start of new up-titration regimen. In case of an interrupted up-titration during a re-initiation, followed by another re-initiation, the subject is considered as having two re-initiations. Interruptions of > 3 days without new up-titration regimen are not counted as re-initiations, but will be flagged in the data. All relevant re-initiation information will be included in the exposure (ADEX) domains.

Re-initiations during the core study are used as derived in the core study ADaMs and not rederived.

The first administration of ponesimod at the start of the extension study is not considered to be a re-initiation.

5.4.1.1.8. Study completion/discontinuation

Study discontinuation/completion in the core study is used as derived in the core study. See the core study SAP for details.

For an individual subject, extension EOS is reached when treatment has been completed/discontinued and safety follow-up (FU) has been completed. Thus, a subject is considered to have completed the study per protocol if they perform the EOS visit as scheduled (30–44 days after the permanent discontinuation of study treatment), even if they prematurely discontinued from study treatment. However, study withdrawal can happen at any time between premature treatment discontinuation/completion and the EOS/FU assessment. Such subjects are considered to have discontinued from the study, even if they completed treatment. Reasons for and date of study discontinuation are captured on the eCRF page "Study Discontinuation".

Possible reasons for study withdrawal are as follows:

- Death;
- Lost to follow-up;
- Subject decision/ withdrawal of consent (further split into: Adverse event, Lack of efficacy, No reason provided, Other);
- Physician decision (further split into: Adverse event, Lack of efficacy, Other);
- Sponsor decision (further split into: Study termination, Other).

5.4.1.2. Analysis of extent of exposure

5.4.1.2.1. Exposure

Exposure to ponesimod treatment will be summarized descriptively, both for the Combined Analysis Period using the FAS (only for subjects included in the SAF who were initially treated with ponesimod 20 mg in the core study) and for the Extension Analysis Period by core study treatment group and overall, using the EXTS, as follows:

- Treatment exposure (months): descriptive statistics;
- Treatment exposure (months) by category (cumulative): frequency counts and percentages;
- Total subject years exposure

- Treatment exposure (months) excluding interruptions: descriptive statistics;
- Cumulative duration of interruptions: descriptive statistics;
- Number of treatment interruptions > 3 days: frequency;
- Number of subjects with at least 1 treatment interruption > 3 days: frequency counts and percentages;
- Number of subjects with at least 1 treatment re-initiation: frequency counts and percentages;
- Number of subjects with at least 2 treatment re-initiation: frequency counts and percentages;

5.4.1.2.2. Compliance with study treatment

Compliance with ponesimod treatment is summarized using descriptive statistics for continuous and categorical data both for the Combined Analysis Period using the FAS (only for subjects included in the SAF who were initially treated with ponesimod 20 mg in the core study) and for the Extension Analysis Period by core study treatment and overall, using the EXTS. Exposure and compliance are also presented in a subject data listing.

5.4.2. Adverse Events

5.4.2.1. General consideration in adverse events

An AE is any event reported by the investigator on the Adverse Event eCRF.

AEs that started in the core study and were still ongoing on Day 1 of the extension study are reported in the 'Ongoing Adverse Events from AC-058B301' extension eCRF form. If the event worsened in intensity/seriousness after start of study treatment in the extension study, such an event was reported in the usual Adverse Event eCRF Form.

All AEs are coded using the MedDRA dictionary (version 26.0).

For the summaries on the Combined Analysis Period, AEs from core and extension study (specifically AEs included in the extension eCRF as 'ongoing' from the core study and the original AEs included in the core eCRF) will be merged using a dedicated ID linking variable included in the related SDTM datasets. The following rules will be used by merging the SDTM datasets:

- If information regarding the seriousness of an ongoing AE is inconsistent between the two databases, the AE is conservatively considered to be serious;
- The outcome as entered in extension study will be used for the analysis;
- If the action taken for an ongoing AE is given as temporarily interrupted in the core study database, and the action taken is missing, none, not applicable, or unknown in the extension study database, then the value from the core will be retained. For all the other cases the action taken as entered in extension study will be used for the analysis;
- If an event entered on the form "Ongoing adverse events from AC-058B301" eCRF page in the extension, this AE will not be considered as treatment-emergent with respect to the Extension Analysis Period, and no dates or other variables will be imputed if missing or partial. Such events will appear in listings only.

For the Combined Analysis Period, cumulative data such as AEs and SAEs will only be summarized for subjects initially treated with ponesimod 20 mg in the core study.

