1.1.1. Safety objectives and endpoints

- To describe the long-term safety and tolerability of ponesimod 20 mg in subjects with Relapsing Multiple Sclerosis (RMS).
- To describe the effects of re-initiation of ponesimod treatment after interruption in subjects with RMS.

Table 2 details the endpoints that will be analyzed for the Extension Analysis Period and for the Combined Analysis Period. See Section 5.1.5 for further details regarding the analysis strategy for safety.

Table 2: Safety endpoints

Endpoints	Combined Analysis Period	Extension Analysis Period
Adverse events		
• Treatment-emergent AEs, SAEs, and AESIs #	Y*	Y
AEs leading to premature discontinuation of study treatment	Y	Y
Cardiac safety		
• Treatment-emergent morphological ECG abnormalities (as defined by the ECG provider)	Y*	Y
 Absolute values by visit for 12-lead ECG parameters (HR, PR, QRS, QT, QTcB, QTcF) 	Y	Y
 Change from baseline values by visit for ECG parameters (HR, PR, QRS, QT, QT QTcB, QTcF) 	Y	Y
• Change in ECG parameters (HR, PR, QRS, QT, QT QTcB, QTcF) from predose to selected post-dose assessments (1 h, 2 h, 3 h, 4 h) on day of re-initiation of study treatment	N	Y

Pulmonary safety

Table 2: Safety endpoints

Endpoints	Combined Analysis Period	Extension Analysis Period
• Absolute values and percent change from baseline in FEV ₁ and FVC at all assessments	Y	Y
• Treatment-emergent decrease from baseline > 20% and >30% in FEV ₁ or FVC	Y*	Y
• Treatment-emergent decrease from baseline > 20 percentage points in % of predicted FEV ₁ and FVC	Y*	Y
• Change in lung diffusion capacity as assessed by DL _{CO} (at selected sites only) expressed in absolute change (mL) and % of predicted value from baseline at all assessments	Y	Y
Other endpoints		
• Absolute values and change from baseline for HR, SBP, DBP, and body weight at all assessments	Y	Y
Treatment-emergent notable blood pressure abnormalities	Y*	Y
• Absolute values and change from baseline for laboratory tests (hematology, blood chemistry) at all assessments	Y	Y
Treatment-emergent notable laboratory abnormalities	Y*	Y

^{*} Cumulative safety data, e.g., AEs for the combined Analysis Period will only be presented for subjects who received 20 mg ponesimod in the core study.

Analyses on the Combined Analysis Period use the core baseline as a reference, while analyses on the Extension Analysis Period use the extension baseline as a refence.

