5.4.2.2.4. Adverse events leading to permanent discontinuation of study treatment

An AE is considered to be an AE leading to discontinuation if the field "Action taken with study drug" is answered "Permanently discontinued" in the eCRF module 'Adverse Event'.

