5.4.2.3.1. Adverse events

Unless otherwise specified, all the AE summaries described below are produced for the Combined Analysis Period (only for subjects included in the SAF who were initially treated with ponesimod 20 mg in the core study) and for the Extension Analysis Period by core study treatment and overall, using the EXTS.

An overview of TEAEs is presented, per study treatment group, as the number and percentage of subjects having any AE, any severe AE, any drug-related AE, any AE leading to study drug discontinuation, any SAE, any drug-related SAE, or any fatal SAE. Similarly, an overview of TEAEs per 100 subject-years is also presented.

The following summary tables will be created to present the frequency and percentage of subjects with any AE, an AE in each primary SOC, and each individual AE (preferred term). SOCs are sorted by descending order of frequency in the ponesimod arm. If the frequencies of SOCs are the same, alphabetical order is used. The same rule applies for preferred terms within SOC:

- All AEs;
- TEAEs;
- TEAEs per 100 subject-years; TEAEs with onset on Day 1 of a re-initiation (all re-initiations summarized together, for subjects with at least one re-initiation), Extension Analysis Period only:
- TEAEs leading to permanent discontinuation of study treatment;
- TEAEs considered to be related to study drug;
- Severe TEAEs;
- Post-treatment AEs (subjects that entered the period between EOT date + 16 and EOS), Extension Analysis Period only.

The following summary tables will also be produced, presenting the frequency and percentage of subjects with any AE, and each individual AE (preferred term) by descending frequency:

CONFIDENTIAL – FOIA Exemptions Apply in U.S.

- TEAEs;
- TEAEs per 100 subject-years;
- TEAEs leading to permanent discontinuation of study treatment;

• TEAEs reported in \geq 5% of subjects in any group (after rounding into the 1st decimal in percentage, e.g. an event occurring in 4.955% of subjects will be rounded to be 5.0% and therefore be included in this summary table).

The following summary tables will also be produced, presenting the frequency and percentage of subjects with any AE, and each individual AE (preferred term) by maximum intensity:

• TEAEs.

AEs (preferred terms) reported more than once in a subject during the period summarized are counted once in frequency tables. Percentages are based on the SAF (ponesimod subjects) or on the EXTS as applicable.

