 - the time of the study drug intake at re-initiation in the extension study, if the onset date equals the date of a documented study drug re-initiation.
 - 00:00, for any other onset date.
- Onset date is completely missing: considered to be treatment-emergent. The onset date and time are imputed as date and time of the first study drug intake in the extension study.

AEs with missing or partial onset date may be considered to be treatment-emergent as per the definitions above. However, they are not considered to be "Day 1" AEs and will not appear in summaries of AEs on Day 1.

For AEs reported on the "Ongoing Adverse Events from AC-058301" eCRF page for the extension study, no dates are imputed and the events are considered to be not treatment-emergent with respect to the Extension Analysis Period.

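### A core-study AE that does not worsen but ends ponesimod in the extension is left out of the extension AE tables, so AEs leading to discontinuation can be under-counted

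*SAP*

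**What the plan says.** Table 2 (Section 1.1.1) lists "AEs leading to premature discontinuation of study treatment" and marks it for both the Combined and the Extension Analysis Period. The row above it is qualified as treatment-emergent and carries an asterisk that limits the combined data to core ponesimod subjects. The discontinuation row has neither.

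Section 5.4.2.1 describes a form for AEs ongoing from the core study. For an event on it, "this AE will not be considered as treatment-emergent with respect to the Extension Analysis Period", and "Such events will appear in listings only". Appendix 13 (Section 6.13.3.1) repeats that "the events are considered to be not treatment-emergent with respect to the Extension Analysis Period". There is one route out: "If the event worsened in intensity/seriousness after start of study treatment in the extension study", it is reported on the usual Adverse Event form.

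For the Combined Period, core and extension records of the same event are merged. The core action is kept in one case: a temporary interruption in the core with an uninformative entry in the extension. Otherwise, "For all the other cases the action taken as entered in extension study will be used for the analysis". Combined AE summaries cover only subjects who received ponesimod in the core study (Sections 5.1.2, 5.4.2.1 and 5.4.2.3.1).

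Section 5.4.2.2.4 identifies an AE leading to permanent discontinuation from the action-taken field of the Adverse Event module. Section 5.4.2.3.1 plans the table for "TEAEs leading to permanent discontinuation of study treatment", and Section 5.4.2.3.4 refers back to it.

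**The concern.** Treatment emergence depends on when an event began. Leading to discontinuation depends on what was done about it. An AE that began in the core study, persisted at the same intensity and seriousness, and then made the subject stop ponesimod in the extension fits the Table 2 endpoint as worded. The tabulation rules nevertheless filter it out by onset.

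Discontinuation because of an AE is a main tolerability measure in a long-term, open-label extension. Any omission of this kind can only lower the tabulated count. The two core arms are also treated differently: an event in a continuous-ponesimod subject has a second chance in the combined table, and one in a switcher does not. Section 5.1.5.2 nevertheless sets out to investigate changes in safety after the switch from teriflunomide. Appendix 2 (Section 6.2.1) does not list the narrowing of the endpoint among its changes to planned analyses.

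**Working it through.** The SAP gives no figure to reproduce, so the check follows one carried-over AE that ends extension ponesimod through the stated rules.

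1. *Entry.* The AE is ongoing on extension Day 1 and goes on the ongoing-AE form (5.4.2.1).
2. *Does it worsen?* If so, it is also reported on the ordinary form and can enter the extension treatment-emergent tables. If not, the SAP names no route to the ordinary form.
3. *Is it treatment-emergent in the extension?* On the ongoing form, no (5.4.2.1 and 6.13.3.1).
4. *Is its action taken read?* Section 5.4.2.2.4 looks only at the Adverse Event module. The merge rule in 5.4.2.1 presupposes that the extension database holds an action taken for these events, so the information is expected to exist.
5. *Is it tabulated?* The discontinuation tables take treatment-emergent events only (5.4.2.3.1 and 5.4.2.3.4).
6. *Does the combined table catch it?* Only for core ponesimod subjects, through the merged action taken, if the event is treatment-emergent relative to the first core dose.
7. *Does anything else show it?* The disposition table gives reasons for treatment discontinuation on the EXTS by core arm (5.2.2.2), and adverse event is a sub-reason under subject and physician decision (5.4.1.1.5). That table carries no AE term, system organ class or seriousness. The listings show the event.

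| Carried-over AE that ends ponesimod | Extension AE tables | Combined AE tables | Disposition by reason | Listings |
|---|---|---|---|---|
| Worsened, ponesimod/ponesimod | can be counted | can be counted | yes | yes |
| Worsened, teriflunomide/ponesimod | can be counted | arm not included | yes | yes |
| Not worsened, ponesimod/ponesimod | no | can be counted | yes | yes |
| Not worsened, teriflunomide/ponesimod | no | arm not included | yes | yes |

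The table of all AEs in Section 5.4.2.3.1 does not rescue the last two rows, because 5.4.2.1 limits these events to listings. Those two sections need reconciling in any case.

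*Scale.* Section 3 gives 877 enrolled subjects. One missed subject is 1/877 = 0.00114, or 0.11 percentage points of the overall extension percentage. If 1 to 10 subjects were missed (an assumption, since the SAP gives no count), the shortfall would be 0.11 to 10/877 = 1.14 points. The denominator in 5.4.2.3.1 is the EXTS, whose size is not stated; 877 is its upper bound. Within one core arm the denominator is smaller and the effect per subject larger.

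**The case against.** The strongest defence is that the rule is deliberate and consistent. Section 5.4.2.3 sets treatment-emergent data as the default for tables, and Section 5.4.2.2.2 defines emergence relative to the first dose of the period. An unchanged event that began earlier is not emergent under that definition. Table 2 can be read as an overview that later sections make operational. For a switcher, a carried-over AE began before any extension ponesimod, so counting it as a ponesimod event could misattribute it. All analyses are exploratory (Section 2).

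Much of this stands. The treatment-emergent definition need not change, and the misattribution point is a good reason to keep such events on their own line. It does not explain why an endpoint without that qualifier is tabulated only with it, when the stopping of ponesimod took place in the extension.

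The check also rests on something not shown: how sites recorded an unchanged event that led to permanent discontinuation. If they re-entered it on the ordinary form, the gap would be smaller or absent. The SAP mentions re-entry only for worsening.

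A reader might infer more than the SAP supports:
- *That all carried-over AEs are barred from extension tables.* Worsened events go to the ordinary form.
- *That such discontinuations in switchers appear in no table.* They appear in no AE table, but disposition counts them.
- *That the AE and disposition tables must disagree because of this rule.* They may, but no such event is shown to exist. The two tables also count different things: disposition has separate categories for death and for pre-specified discontinuation criteria.
- *That tolerability is in fact overstated by a known amount.* No count supports that.

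**Conclusion.** The point holds for carried-over AEs that do not worsen but end ponesimod in the extension. Under the stated rules they are excluded from the Extension Period discontinuation tables, and for teriflunomide switchers from the AE tables of both periods. The Table 2 endpoint can therefore be under-counted, in one direction only. The size is unknown, at about 0.11 percentage points overall per missed subject. The conclusion assumes that such events stay on the ongoing form and that their action taken is held in the extension database, as the merge rule implies. The effect is probably small, but this is a named tolerability endpoint and the correction is cheap, so it should be made.

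**What to change.** Keep the treatment-emergent discontinuation table as planned. Add a separate line to it, by core arm and overall, labelled as started in core and ongoing at extension start. It should count AEs and SAEs on the ongoing-AE form whose extension action taken is permanent discontinuation. To allow this, extend Section 5.4.2.2.4 to that form, add the exception to the listings-only sentence in Section 5.4.2.1, and reconcile that sentence with the all-AEs table in Section 5.4.2.3.1.

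If the sponsor prefers not to add the line, the minimum is to limit the Table 2 endpoint to treatment-emergent events and declare this in Appendix 2. That makes the plan consistent but leaves these discontinuations without an AE term in any table for switchers.

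The cost is a few sentences of SAP wording and one selection condition in programming. The reported number of discontinuation AEs may rise slightly. For switchers the added line will include events that began before extension ponesimod, which is why it needs its own label and should not be added to the treatment-emergent count.

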5.4.2.2. Analysis variables in AE

5.4.2.2.1. Frequency of adverse events and AEs per 100 subject-years

AEs are summarized according to both frequency (number of subjects and percentages) and AEs per 100 subject-years (number of events and rate) and based on various grouping terms (for example MedDRA preferred term, or MedDRA primary system organ class).

For frequency of subjects experiencing an AE, AEs reported more than once for a subject within the Analysis Period (based on grouping term) are counted only once per subject.

AEs per 100 subject-years = Total cumulative number of events during the Analysis Period / Cumulative observation time in the treatment-emergent period over all subjects (100 years) per grouping term.

For total cumulative number of events, multiple records of the same MedDRA preferred term in the AE dataset for the same subject count as individual events (episodes of the same type of event) unless they have the same start date and, if available, time.

The observation time (in days) per subject for summaries of treatment-emergent AEs is calculated as:

- minimum (extension EOT + 15, extension EOS) ponesimod start date in the extension study
 + 1, for the Extension Analysis Period;
- minimum (extension EOT + 15, extension EOS) ponesimod treatment start date in the core study +1, for subjects in the Combined Analysis Period who had entered extension study.
- minimum (core EOT + 15, core EOS) ponesimod treatment start date in the core study +1, for subjects in the Combined Analysis Period who did not enter extension study.

5.4.2.2.2. Treatment-emergent adverse events

Treatment-emergent adverse events (TEAEs) are defined as AEs occurring from start of treatment up to treatment end date + 15 days.

Treatment-emergence is considered with respect to the relevant Analysis Period, i.e., relative to the first dose of ponesimod in the core study for the Combined Analysis Period, and relative to the first dose of ponesimod in the extension study for the Extension Analysis Period.

AEs with completely missing start date will be considered treatment-emergent. If it is not clear whether the event is treatment-emergent or not (in case of partial dates), the event will be considered treatment-emergent (e.g., start date of AE is documented in the database as May 2016 and treatment start date 23 May 2016, see definition of handling of missing data in Section 6.13.3).

Extension study day of onset

Study day of onset (relative to the start of the extension study) is derived for all TEAEs in the Extension Analysis Period.

TEAEs on Day 1 of re-initiation of ponesimod treatment are those AEs that start at or after the time of the first administration of ponesimod on Day 1 of the re-initiation after study drug interruption, and before the following calendar date. Day of onset relative to the start of a re-

initiation is derived for all treatment-emergent adverse events in the Extension Analysis Period in the same way as described above for extension study day of onset.

AE duration (days)

AE duration in days is derived for all treatment-emergent adverse events with complete start and end dates only as AE end date – AE start date + 1. Furthermore, duration of AE is derived only if both start date and end date are complete.

